Study Protocol

Title of Project: A Message Framing Intervention for Increasing Parental Acceptance of Human Papillomavirus Vaccination

NCT #: NCT03856437

02/10/2021

1. Abstract:

The overall goal of this project is to test the relative efficacy of gain- versus loss-framed messages in promoting adolescent HPV vaccination acceptance among African American parents. This project will provide useful insights into the design of psychologically targeted adolescent HPV vaccination messages for African Americans.

2. Subject Selection:

- a. **Recruitment:** Participants will be recruited from online panels provided by survey companies.
- b. **Eligibility Criteria:** Participants must meet the following criteria: 1) be at least 18 years old; 2) self-identify as African American; 3) be a custodial parent or caretaker of at least one child who has not initiated or completed the HPV vaccine series.
- c. **Rationale:** African American women are more likely to develop cervical cancer and die from cervical cancer, a disease that can be prevented from the HPV vaccine. Understanding effective methods of communicating to African American parents about the importance of HPV vaccination is therefore critical.
- d. **Enrollment Numbers:** We plan to enroll approximately 2,000 participants.
- e. **Rationale for Enrollment Numbers:** A large sample size ensures adequate statistical power to detect even small effect sizes.

3. Procedures:

Participants will complete a computer-assisted survey. In the survey participants will first answer questions related to their beliefs about HPV and the HPV vaccine, as well as other background information. Then they will be presented with a gain-framed, a loss-framed, or a non-framed HPV vaccination message. After message exposure, they will answer questions related to their attitudes toward HPV vaccination, intentions to vaccinate their children, as well as other message response measures. The survey will take approximately 20 minutes. Participants will be compensated by the survey companies in accordance to their policies.

4. Risks:

There are no known risks associated with this research. Some participants may be uncomfortable answering some questions. All participants have the option of not responding to questions they do not wish to answer.

5. Benefits:

Study Protocol

Title of Project: A Message Framing Intervention for Increasing Parental Acceptance of Human Papillomavirus Vaccination

NCT #: NCT03856437

02/10/2021

There are no direct benefits to participants. This research will result in an improved understanding of the design of effective educational materials about HPV vaccination.

6. Confidentiality:

Responses of the participants will be confidential. The questionnaires will not contain any questions that ask for information that could be used to identify the participants. The online survey will be anonymous. Only approved researchers will have access to the data collected. Data collected will be stored in a password-protected computer located in a room with limited access. All research data collected from this study will be stored for 10 years after the study and allow the research team to thoroughly analyze the data for research purposes only. The research data will be destroyed afterwards (removed from computer hard disks).

7. Consent Process:

Before the participants begin the study, they will be asked to read a consent form containing information on the purpose of the study, the procedures involved, confidentiality, and potential risks and benefits. It will also state that participants can withdraw from the study at any time if they feel uncomfortable with the survey. Participants will have the choice to continue with the study or not after reading the consent form.

8. Conflict of Interest:

There is no conflict of interest.

9. HIPAA Compliance:

N/A

10. Research Outside of the United States:

N/A

11. Research Involving Prisoners:

N/A

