Statistical Analysis Plan

Title of Project: A Message Framing Intervention for Increasing Parental Acceptance of Human Papillomavirus Vaccination
NCT #: NCT03856437
04/21/2022

We will conduct Analyses of Covariance (ANCOVAs) and multiple regressions to examine the group differences. The primary dependent variables will consist of parents' attitudes and intentions toward vaccinating their children against HPV (both are continuous variables). Secondary dependent variables will consist of message evaluation variables. In ANCOVAs, the key independent variable will be framing (gain, loss, no frame). Covariates will include key demographic variables such as age, gender, and baseline vaccine attitudes. We will also examine whether the effects of framing will vary as a function of other characteristics of the message (e.g., whether it contains an image and the valence of the image) by examining their interactions. In regression analyses, a block structure will be used where the first block will consist of the control variables (i.e., covariates) and the second block will contain the key predictor variable—framing. In regression analyses, we will also examine whether the effects of framing vary as a function of recipient characteristics such as their initial beliefs about the vaccine. The moderated multiple regression (MMR) technique will be used to construct the interaction terms, wherein each interaction term is formed after the component variables have been centered. This procedure is used to reduce multicollinearity, which could result in inflated standard errors for coefficient estimates. We will also report standard descriptive statistics and correlation matrices for all key variables.

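### Do the unquantified power statement and the reason given for centering leave the planned moderation tests misdescribed?

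*Protocol*

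**What the plan says.** Protocol section 2.d gives the size ("We plan to enroll approximately 2,000 participants") and section 2.e gives the whole rationale: "A large sample size ensures adequate statistical power to detect even small effect sizes". It states no alpha, target power, effect metric or test. Section 3 describes three message conditions without an allocation ratio.

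The SAP, a single paragraph, makes framing the main factor in the ANCOVAs and the second block in the regressions. The outcomes are attitudes and intentions ("both are continuous variables"). On adjustment it says: "Covariates will include key demographic variables such as age, gender, and baseline vaccine attitudes".

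Moderation comes in two places. After the ANCOVA sentences, framing is to be crossed with "other characteristics of the message (e.g., whether it contains an image and the valence of the image"). In the regression part, framing is to be crossed with recipient characteristics such as prior beliefs. Centering is described only in that regression part, and the reason given is: "This procedure is used to reduce multicollinearity, which could result in inflated standard errors for coefficient estimates".

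**The concern.** The power sentence has no limits, so a reader could apply it to every planned test. An interaction between framing and image compares two differences, so its standard error is much larger than that of a simple arm comparison. A sample that is generous for the main effect can be modest for the interaction.

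The stated reason for centering seems to offer reassurance about precision in the moderation regressions. For the interaction term that reassurance is empty, because centering only reparametrises the model.

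Taken together, the two sentences might lead someone to report a non-significant interaction as evidence that framing works alike with or without an image and at every level of belief. The project aims to inform targeted messages, so that would be a substantive error.

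**Working it through.** **Inputs.** From the documents: total N about 2,000, three message conditions, continuous outcomes, covariate adjustment. Assumed, because the documents do not say: equal allocation (2,000/3 = 667 per arm), outcome SD 1, two-sided alpha 0.05, either two image levels (6 cells of 333) or three (9 cells of 222), and no item non-response. The plan gives no power figure to reproduce.

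**Framing main effect.** SE = sqrt(2/667) = 0.0548. At 0.20 SD: 0.20/0.0548 = 3.65, and 3.65 − 1.96 = 1.69, so power is 95%. The smallest difference with 80% power is 2.80 × 0.0548 = 0.153 SD.

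**Change in the gain-loss gap between two image conditions.** SE = sqrt(4/n per cell).

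| Layout | SE | Power at 0.20 SD | Detectable at 80% |
|---|---|---|---|
| 3×2, 333 per cell | 0.110 | 45% | 0.307 SD |
| 3×3, 222 per cell | 0.134 | 32% | 0.376 SD |

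Covariates multiply the SE by sqrt(1 − R²). At R² = 0.30, power becomes 59% (3×2) and 43% (3×3). At R² = 0.50 it becomes 73% and 56%, and the detectable change falls to 0.307 × 0.707 = 0.217 SD and 0.376 × 0.707 = 0.266 SD. The R² values are assumptions.

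**Beliefs as a continuous moderator.** For a gain-loss difference in slope per SD of beliefs, SE = sqrt(2/667) = 0.0548. Power is 45% at 0.10 per SD and 95% at 0.20 per SD.

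**The same examples in a common metric.** Cohen's f² is the mean squared interaction effect over cells, in SD units. The no-frame arm is set at zero and the gain and loss effects are symmetric.

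- 0.20 change in gap, 3×2: four cells at ±0.05, f² = 4 × 0.0025/6 = 0.00167, f = 0.041.
- 0.20 change between two of three image levels: f² = 4 × 0.0025/9 = 0.00111, f = 0.033.
- 0.20 gap in one of three image levels only: f² = 0.02 × (2/3)/9 = 0.00148, f = 0.038. The noncentrality is 2,000 × 0.00148 = 2.96, and the 4-df test has 24% power.
- Beliefs, 0.10 per SD: f² = 2 × 0.0025/3 = 0.00167, f = 0.041.
- For comparison, a 0.20 SD gain-loss main effect: f² = (0.01 + 0.01)/3 = 0.00667, f = 0.082.

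The low-power examples are therefore half or less of a 0.20 SD main effect on this scale. At the usual small benchmark, f = 0.10, power is 98.5% for a 2-df interaction and 96% for a 4-df one.

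**Centering.** Write y = b0 + b1·F + b2·M + b3·F·M, and replace F and M by their deviations from their means. The coefficient of the product stays b3, while the framing coefficient becomes b1 + b3 × (mean of M). The fit is the same. One simulated data set of 2,000 records with two framing contrasts confirmed this:

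| Quantity | Raw | Centered |
|---|---|---|
| Interaction estimates | 0.1053, 0.0094 | 0.1053, 0.0094 |
| Interaction SEs | 0.0450, 0.0448 | 0.0450, 0.0448 |
| Interaction t values | 2.342, 0.210 | 2.342, 0.210 |
| Interaction variance inflation | about 16.5 | about 1.4 |
| Framing SE (lower order) | 0.186 | 0.055 |
| Moderator SE (lower order) | 0.033 | 0.018 |

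The lower-order standard errors fall because those coefficients now describe effects at the average of the other variable.

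**The case for a change.** The best case for a change is that it would cost only words. Section 2.e does not confine itself to main effects, and moderation matters to the project's purpose. An attenuated framing effect is a plausible form of interaction, and it is poorly covered: 80% power for a 0.20 SD change in gap with two equal image levels would need 6 × 4 × 7.85/0.04, or about 4,710 participants. The f = 0.10 benchmark is also less modest than it sounds. In a 3×3 layout, 4a²/9 = 0.01 gives a = 0.15, which for example is a gap swinging from +0.30 to −0.30 SD. Permitted item non-response would lower power further.

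All of that arithmetic stands, as does the observation that the sentence is unquantified and that centering is better defended by interpretability.

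Four parts of the argument do not stand. First, section 2.e makes no claim about a 0.20 SD difference of differences; that target is supplied by the reader. Second, centering is not the only aid to precision, because the SAP adjusts for covariates that include baseline vaccine attitudes, and it describes centering for the regression interactions, not for the image ANCOVAs. Third, the centering sentence speaks of coefficient estimates in general and is right about the lower-order ones. Fourth, neither document commits anyone to reading a null interaction as no moderation.

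**Conclusion.** No change is needed. The sample-size sentence is vague, but it is not contradicted by the design: it holds for the framing comparison that the abstract and SAP put first (95% power at 0.20 SD) and for a conventionally small interaction. It would fail only if read as covering a change in gap of about 0.20 SD (32% to 45% power without covariates, up to 73% if they explain half the variance).

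A fuller statement would have to import an allocation ratio, alpha, number of image levels and R², none of which the documents give. The detectable change in gap would range from about 0.22 to 0.38 SD depending on those choices. The centering rationale is loosely worded but harmless, since the procedure gives the same interaction test either way. An analyst following the plan obtains the same interaction results, and their standard errors show how much a null finding can support.

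These figures rest on equal cells, unit SD, two-sided 0.05 and complete responses. The conclusion that centering does not affect the interaction test is algebra and needs none of those assumptions.

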Statistical Analysis Plan

Title of Project: A Message Framing Intervention for Increasing Parental Acceptance of Human Papillomavirus Vaccination
NCT #: NCT03856437
04/21/2022

We will conduct Analyses of Covariance (ANCOVAs) and multiple regressions to examine the group differences. The primary dependent variables will consist of parents' attitudes and intentions toward vaccinating their children against HPV (both are continuous variables). Secondary dependent variables will consist of message evaluation variables. In ANCOVAs, the key independent variable will be framing (gain, loss, no frame). Covariates will include key demographic variables such as age, gender, and baseline vaccine attitudes. We will also examine whether the effects of framing will vary as a function of other characteristics of the message (e.g., whether it contains an image and the valence of the image) by examining their interactions. In regression analyses, a block structure will be used where the first block will consist of the control variables (i.e., covariates) and the second block will contain the key predictor variable—framing. In regression analyses, we will also examine whether the effects of framing vary as a function of recipient characteristics such as their initial beliefs about the vaccine. The moderated multiple regression (MMR) technique will be used to construct the interaction terms, wherein each interaction term is formed after the component variables have been centered. This procedure is used to reduce multicollinearity, which could result in inflated standard errors for coefficient estimates. We will also report standard descriptive statistics and correlation matrices for all key variables.

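### The SAP names pre-message HPV beliefs only as a moderator; adding them as a covariate in the primary models may gain precision at almost no cost.

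*SAP*

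**What the plan says.** Protocol section 3 (Procedures) sets the order of the survey. Before the message, "participants will first answer questions related to their beliefs about HPV and the HPV vaccine, as well as other background information". The outcomes follow: "After message exposure, they will answer questions related to their attitudes toward HPV vaccination", together with intentions and other message responses.

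The SAP makes attitudes and intentions toward HPV vaccination the two primary outcomes, both continuous, and compares three framing groups by ANCOVA and multiple regression. On adjustment it says: "Covariates will include key demographic variables such as age, gender, and baseline vaccine attitudes". The regressions enter these same covariates first and framing second. Beliefs appear once in the SAP, where the regressions are to examine whether framing effects depend on "recipient characteristics such as their initial beliefs about the vaccine".

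The SAP does not say whether baseline vaccine attitudes are general or specific to HPV, or whether they overlap with the belief items. Protocol section 4 (Risks) lets participants leave any question unanswered. The SAP gives no rule for missing baseline items.

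**The concern.** Both primary outcomes concern the HPV vaccine. The only HPV-specific measure that the protocol names before exposure is beliefs, and a parent's prior beliefs about this vaccine are a plausible predictor of attitude and intention measured minutes later. The SAP assigns that measure to moderation and names a differently worded measure as the covariate.

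If beliefs explain outcome variation that age, gender and baseline vaccine attitudes leave unexplained, omitting them makes the confidence intervals for the framing contrasts wider than the data require. That matters to the plan's own aim, since protocol section 2e justifies the enrollment by saying that "A large sample size ensures adequate statistical power to detect even small effect sizes". For small effects, a modest change in the standard error can move power by several points. The stake is efficiency alone.

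**Working it through.** **The plan's own figure.** Protocol section 2d says "We plan to enroll approximately 2,000 participants". This number cannot be reproduced, because no effect size, SD, significance level, power or covariate R-squared is given.

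**Assumptions for illustration.** Random allocation 1:1:1 (neither document states the method or the ratio), so n = 2000/3, about 667 per arm; two-sided 5%; 80% power; normal approximation. The unit is the residual SD after the covariates already planned.

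**Step 1, without beliefs.** Detectable pairwise difference = (1.960 + 0.842) × sqrt(2/667) = 0.153. Power for a difference of 0.15 is 78.2%.

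**Step 2, with beliefs added.** Let p be the partial R-squared of beliefs given the planned covariates. The standard error is multiplied by sqrt(1 − p), and effective N is 2000/(1 − p).

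| Assumed p | SE multiplier | Effective N | Detectable difference | Power at 0.15 |
|---|---|---|---|---|
| 0 | 1.000 | 2,000 | 0.153 | 78.2% |
| 0.01 | 0.995 | 2,020 | 0.153 | 78.6% |
| 0.05 | 0.975 | 2,105 | 0.150 | 80.2% |
| 0.10 | 0.949 | 2,222 | 0.146 | 82.3% |
| 0.20 | 0.894 | 2,500 | 0.137 | 86.5% |

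The SE multiplier does not depend on the significance level, so it also holds under a multiplicity adjustment.

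**Step 3, how p depends on overlap with baseline attitudes.** Let a and b be the correlations of attitudes and beliefs with the outcome, and c the correlation between the two. Then R² = (a² + b² − 2abc)/(1 − c²), and p = (R² − a²)/(1 − a²). All correlations here are assumed.

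- a = b = c = 0.5: R² = 0.25/0.75 = 0.333; p = 0.083/0.75 = 0.111; effective N 2,250.
- a = b = 0.5, c = 0.9 (nearly the same measure): p = 0.018; effective N 2,036.
- a = 0.5, b = 0.3, c = 0.5: p = 0.004; effective N 2,009.
- a = 0.3 (general, weakly related attitudes), b = c = 0.5: p = 0.179; effective N 2,438.

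These scenarios run from about 9 to about 440 participants' worth. A stronger assumed b gives more: a = c = 0.5 with b = 0.6 gives 2,557. If the two measures are the same scale, p = 0.

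**Step 4, skipped items.** If participants with missing beliefs were dropped, effective N would be 2000(1 − m)/(1 − p), where m is the fraction missing. The gain vanishes when m = p. At p = 0.05, 5% missing gives 2000 × 0.95/0.95 = 2,000, and 10% missing gives 2000 × 0.90/0.95 = 1,895, a net loss.

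**The case against.** The strongest reply is that the SAP excludes nothing. Its covariate list is given by example, a moderator may also be a covariate, and an outcome-like baseline is already planned. This stands in part. A reader might infer that beliefs are barred from the primary models, but the text says only that they are not named there. Only the increment over baseline vaccine attitudes can be lost. If those planned covariates already explain 25% of the outcome variance (assumed), power at 0.15 outcome SD is about 88%, and adding beliefs at p = 0.05 raises it only to about 90%. An open list, however, does not commit the analyst to using beliefs.

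Three stronger readings are tempting, and the documents do not support them:

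- **The moderator's own term is missing from the model.** The SAP specifies moderated multiple regression and centers the components to limit collinearity with their product. That makes sense only if the components are in the model too. It does not settle the separate primary ANCOVAs.
- **A post-message attitude score might serve as the baseline covariate.** The SAP calls the covariate baseline, and the protocol's pre-message part also covers unspecified background information, which could include it.
- **Adjustment would remove bias from break-off.** The documents give no break-off data. Whether adjustment would help depends on how break-off relates to arm and beliefs.

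The reply is also right that adjustment is not free of conditions: items may be skipped, and Step 4 shows that dropping cases could cancel the gain.

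**Conclusion.** The point holds as a possible loss of precision. Given random allocation, the planned comparisons are valid with or without beliefs in the model, and there is no arithmetic error in the plan. The primary ANCOVAs and regression block 1 do not commit to an HPV-specific baseline measure that the survey already plans to collect.

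The size cannot be found from the documents. For an assumed partial R-squared of 0.01 to 0.20 beyond the planned covariates, the standard error falls by about 0.5% to 11%. The gain is nil if beliefs and baseline vaccine attitudes are one scale, and likely largest if those attitudes are general and only weakly related to the outcomes. Since the change costs almost nothing, it is worth making even if the gain proves small.

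**What to change.** In the SAP:

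1. Add the pre-message HPV and HPV-vaccine belief score, or its few sub-scores, as a covariate in every primary ANCOVA and in regression block 1, beside age, gender and baseline vaccine attitudes. Define the score, since neither document does. If it is the same scale as baseline vaccine attitudes, say so and enter it once.
2. State that only items answered before the message may serve as covariates.
3. Handle skipped belief items by simple baseline imputation, for example the mean with a missing indicator, so that no participant is dropped for this reason.

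The cost is a few sentences and one or a few degrees of freedom out of about 2,000 participants. No new questions or participants are needed.

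### A framing-by-belief interaction cannot be told apart from a framing-by-baseline-attitude interaction, because the SAP specifies no product of framing with baseline vaccine attitudes

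*SAP*

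**What the plan says.** The SAP is a single section. On covariates it states: "Covariates will include key demographic variables such as age, gender, and baseline vaccine attitudes". For the regressions, "the first block will consist of the control variables (i.e., covariates) and the second block will contain the key predictor variable—framing". The moderation analysis will "examine whether the effects of framing vary as a function of recipient characteristics such as their initial beliefs about the vaccine", using products of centered variables. Centering is justified there only as a way to limit multicollinearity.

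No product of framing with baseline vaccine attitudes, or with any other covariate, is named. The list of moderators is open, with initial beliefs as its only example. The SAP does not say whether several moderators enter one model together or are tested one at a time.

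Protocol section 3 (Procedures) places the belief questions before message exposure, so beliefs are baseline variables.

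**The concern.** Frame is an assigned condition, whereas beliefs are traits that participants bring with them. Initial vaccine beliefs and baseline vaccine attitudes plausibly overlap. Entering baseline attitude as a control adjusts the level of the outcome; it does not adjust the size of the framing effect. If framing works differently according to baseline attitude, any belief correlated with that attitude carries part of the interaction, although attitude is nominally controlled.

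Neither assigning the frame nor centering the variables removes this. Nor does a larger sample: the borrowed coefficient stays the same while its standard error shrinks.

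What is at stake is the targeting conclusion. Protocol section 1 (Abstract) says the project will give "insights into the design of psychologically targeted adolescent HPV vaccination messages for African Americans". If that guidance names a particular belief as what changes the response to framing, the analysis has to separate the belief from baseline attitude.

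**Working it through.** **The plan's own figure.** Protocol section 2d says "We plan to enroll approximately 2,000 participants", and section 2e supports this with "A large sample size ensures adequate statistical power to detect even small effect sizes". No effect size, alpha, power or SD is given, so the 2,000 cannot be reproduced. For context, three equal arms give about 667 each. At two-sided 0.05 and 80% power, the detectable pairwise difference is (1.960 + 0.842) × √(2/667) = 0.153 SD.

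**Inputs**
- From the documents: about 2,000 participants, three frames, continuous outcomes, baseline attitude as a control.
- Assumed: equal allocation (n = 667 per arm); two-sided 0.05; baseline attitude A and belief B standardized, with correlation r = 0.3, 0.5 or 0.7; a gain-minus-loss difference that changes by d = 0.10 or 0.15 outcome units per SD of A; B with no moderating effect of its own; outcome = 0.5A + 0.2B + d × (gain-loss code) × A + error, with error SD 0.8.
- Outcome variance is about 0.25 + 0.04 + 0.2r + 0.64 = 0.93 + 0.2r, that is 0.99 to 1.07. One outcome unit is therefore about one SD.

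**Step 1: expected coefficient.** Since the mean of A given B is rB, the gain-loss difference at a given B is d × r × B. With A as a control only, the gain-loss × B coefficient has expectation r × d.

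**Step 2: standard error.** 0.8 × √(2/667) = 0.0438.

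**Step 3: rejection rate.** With z = r × d / 0.0438, the rate is P(Z > 1.96 − z) + P(Z < −1.96 − z). The last two columns are simulated, with 1,500 trials per setting and N = 2,001.

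| d | r | r × d | z | Formula | Simulated, A as control only | Simulated, framing × A added |
|---|---|---|---|---|---|---|
| 0.10 | 0.3 | 0.030 | 0.68 | 10% | 10.1% | 4.7% |
| 0.10 | 0.5 | 0.050 | 1.14 | 21% | 21.7% | 5.3% |
| 0.10 | 0.7 | 0.070 | 1.60 | 36% | 36.5% | 5.4% |
| 0.15 | 0.3 | 0.045 | 1.03 | 18% | 17.5% | 5.0% |
| 0.15 | 0.5 | 0.075 | 1.71 | 40% | 39.7% | 5.6% |
| 0.15 | 0.7 | 0.105 | 2.40 | 67% | 65.1% | 4.2% |

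A repeat simulation gave 10%, 19% and 35% at d = 0.10, and 17%, 39% and 69% at d = 0.15.

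**Step 4: a different test.** This version used a 2-df F test of framing × B, error SD 1, N = 2,000 and 2,000 trials per setting. With A as a control only, the rejection rates at r = 0.3, 0.5 and 0.7 were:
- d = 0.1: 7%, 12%, 18%
- d = 0.2: 16%, 34%, 61%
- d = 0.3: 28%, 67%, 93%

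With r = 0, or with d = 0 (run at r = 0.5), the rate was 5% to 6%. With framing × A added, it was 4.2% to 6.0% throughout.

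**Step 5: precision cost of adding framing × A.** The standard error is multiplied by 1/√(1 − r²), which is 1.05, 1.15 and 1.40. With p equally correlated moderators the multiplier is √[(1 + (p − 2)r) / ((1 − r)(1 + (p − 1)r))]. For four beliefs plus attitude (p = 5):
- r = 0.5: √(2.5/1.5) = 1.29
- r = 0.7: √(3.1/1.14) = 1.65

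**The case against.** The strongest objection is that these rejections are not errors for the question the SAP poses. The SAP asks whether the framing effect differs along a belief. In the calculation it does, by r × d per SD of belief. The single-moderator model answers that question correctly, and a belief that only marks who responds differently may still be useful for targeting. This stands. The error arises only if the belief is then credited as something distinct from baseline attitude.

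A reader might also infer that the SAP restricts covariates to main effects and tests moderators one at a time. It says neither. Baseline attitude is itself a recipient characteristic and could be on the open list, and joint entry is not ruled out. What the text supports is narrower: no framing-by-attitude product and no joint model is specified. Adding attitude as one more single moderator would not separate it from the belief.

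The correlation and the attitude moderation are assumptions, and the rates depend heavily on them. The documents also do not say how far the belief and attitude measures are distinct instruments. Finally, the return to 5% assumes that attitude is measured without error; with measurement error, some of the attitude interaction would still pass to the belief.

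**Conclusion.** The point holds in a limited form. As written, the plan can detect that framing effects differ along a belief, but it specifies nothing that separates the belief from a correlated baseline attitude. With 667 per arm, a gain-loss difference that changes by 0.10 to 0.15 outcome units per SD of attitude, and a correlation of 0.3 to 0.7, a belief with no role of its own is significant in about 10% to 70% of trials, against about 5% with framing by attitude included. If either the attitude moderation or the correlation is zero, there is no such problem.

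A reader might infer that every correlated belief will appear as a moderator, or that the trial's main result is biased. The documents support neither. Over the assumed values, detection is far from certain, and the primary framing comparisons are unaffected. This is a cheap improvement to a supplementary analysis.

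**What to change.** For each moderated regression, also fit the model that adds the products of framing with baseline vaccine attitudes beside framing by belief, and report the two models side by side. Describe a belief as a moderator distinct from baseline attitude only when the joint model supports it. Otherwise describe it as a marker of differential response that cannot be separated from baseline attitude, without dismissing it.

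The cost is SAP wording and one further model per moderated regression. Baseline attitude is already a covariate, so no new data are needed.

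The price is precision: the standard error of the belief interaction rises by about 5%, 15% and 40% at correlations of 0.3, 0.5 and 0.7. Entering several beliefs together costs more: with four beliefs plus attitude, about 29% at 0.5 and 65% at 0.7. Power falls accordingly. In the 2-df simulation at d = 0.2, a true attitude moderator was detected in about 92% of trials when tested alone, and in 88%, 82% and 64% when tested jointly at the three correlations. A non-significant joint result is therefore not evidence of no moderation, and the SAP should say so. For the same reason, a single model holding all beliefs and all covariate products is a trade-off and need not be the default.
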